10. CLINICAL INVESTIGATION INTERVENTION

10.1 Identity of the medical device under investigation

All patients will receive one transfusion episode of at least two units of hypoxic RBCs that were manufactured with Hemanext ONE system.

See section 5.2 for details on the Hemanext ONE system. PRO-CLIN-0012 Rev. AB – 16-MAR-2023

See sections 11.1.1 and 11.1.2 for a detailed list of all information being collected.

10.1.1 Experimental Intervention (medical device)

Units of hypoxic RBCs will be manufactured at Oslo's University Blood Bank or Haukeland University Hospital's Blood Bank using Hemanext ONE system. The hypoxic RBCs manufactured in Oslo will be shipped to the Blood Bank at Haukeland University Hospital where they will be stored at 1-6°C for up to 42 days. Participants who would normally receive a transfusion of units of conventional RBCs will instead receive a transfusion of 2 units of hypoxic RBCs and any additional conventional RBCs as needed. All transfusions will be performed according to the site's SOPs.

10.1.2 Control Intervention (standard/routine/comparator)

Not applicable.

10.1.3 Labelling and Supply

The Hemanext ONE blood processing system (medical device) will be supplied by Hemanext to the Blood Banks after the study contract is executed. All devices will be supplied to the site before start of manufacturing.

The medical device will be a commercial product labelled with CE Mark. The hypoxic blood manufactured by Oslo's or Haukeland's Blood Bank will be labelled (on Hemanext Storage Bag / HSB) per local blood bank, Norwegian Directorate of Health and regulatory requirements, i.e. "Exclusively for Clinical Investigations".

See Appendix section for reference

Hemanext ONE blood processing system may not be used in any capacity until proof of CEC approval for the study have been received by the Sponsor and PI.

10.1.4 Storage Conditions

The Hemanext ONE kits must be stored at room temperature in a secure location. Any exposure of the kits to excessive heat or freezing must be avoided.

The hypoxic RBCs must be stored in cold storage at 1-6°C for up to 42 days.

10.2 Discontinuation or modifications of the intervention

Hemanext may suspend or prematurely terminate either a clinical investigation in an individual investigation site or the entire clinical investigation for significant and documented reasons. A Principal Investigator, DMC, CEC, or regulatory authority may suspend or prematurely terminate participation in a clinical investigation at the investigation sites for which they are responsible. If suspicion of an unacceptable risk to subjects arises during the clinical investigation, or when so instructed by the DMC, CEC, or regulatory authorities, Hemanext shall suspend the clinical investigation while the risk is assessed. Hemanext shall terminate the clinical investigation if an unacceptable risk is confirmed.

Hemanext shall consider terminating or suspending the participation of a particular investigation site or investigator in the clinical investigation if monitoring or auditing identifies serious or repeated deviations on the part of an investigator. If suspension or premature termination occurs, the terminating party shall justify its decision in writing and promptly inform the other parties with whom they are in direct communication. The Principal Investigator and Hemanext shall keep each other informed of any communication received from either the DMC, CEC, or the regulatory authority.

If, for any reason, Hemanext suspends or prematurely terminates the investigation at an individual investigation site, Hemanext shall inform the responsible regulatory authority as appropriate and

ensure that the CEC is notified, either by the Principal Investigator or by Hemanext. If the suspension or premature termination was in the interest of safety, Hemanext shall inform all other Principal Investigators.

If suspension or premature termination occurs,

- Hemanext shall remain responsible for providing resources to fulfill the obligations from the protocol and existing agreements for following up the subjects enrolled in the clinical investigation, and
- the Principal Investigator or authorized designee shall promptly inform the enrolled subjects at his/her investigation site, if appropriate.

When Hemanext concludes an analysis of the reason(s) for the suspension, implements the necessary corrective actions and decides to lift the temporary suspension, Hemanext shall inform the Principal Investigators, the DMC, the CECs, and, where appropriate, the regulatory authority of the rationale and provide them with the relevant data supporting this decision.

Concurrence shall be obtained from the CECs and, where appropriate, regulatory authorities before the clinical investigation resumes. If subjects have been informed of the suspension, the Principal Investigator or authorized designee shall inform them of the reasons for resumption.

10.3 Compliance with clinical investigation intervention

A participant being lost to follow-up will be the main risk of noncompliance in this study. If a participant is lost to follow-up, the investigator will take all necessary measures to re-establish contact with the participant to ascertain the reasons for discontinuation and the participant's state of health. The case report form (CRF) will be completed up to the participant's last visit.

10.4 Data Collection and Follow-up for withdrawn subjects

If a participant withdraws from the study, the investigator will take all necessary measures to establish contact with the participant to ascertain the participant's state of health. The case report form (CRF) will be completed up to the participant's last visit.

10.5 Clinical investigation specific preventive measures

There are no specific recommendations for preventative measures. All standard/routine measures will apply.

10.6 Concomitant Interventions (treatments)

There are no specific recommendations for concomitant interventions. All standard/routine interventions will apply.

10.7 Medical Device Accountability

The Blood Banks will be required to document 100% accountability of the Hemanext One device until all product provided has been used to process hypoxic RBCs, destroyed and/or returned to Hemanext. A "Study Product Receipt and Disposition Log" will be supplied by Hemanext in the Clinical Trial Binder at the Blood Banks for documenting each receipt and disposition (i.e., used, discarded or returned) of the medical device.

The hypoxic RBC product will be tracked via the Oslo and Bergen Blood Bank standard practice. The clinical site will record the hypoxic RBC product information in the Subject's source documents.

10.8 Return, Analysis or Destruction of the Medical Device

Unused Hemanext ONE medical device will be returned to the sponsor at the end of the trial or destroyed according to local procedures, unless other documented instructions are provided in advance to the clinical site.

In case of device deficiencies, including malfunction, usability issues, or inadequacy in the information supplied by the manufacturer including labelling, the devices will be returned to the sponsor for analysis.

11. CLINICAL INVESTIGATION ASSESSMENTS

The following information will be collected, from enrollment throughout end of study visit, when applicable:

- 1. Patient consent
- 2. Inclusion/Exclusion criteria
- 3. Demographics
- 4. Medical history
- 5. Physical examination
- 6. Pregnancy test (if applicable)
- 7. Height
- 8. Weight
- 9. RBC unit weight and volume
- 10. Age of the RCC unit at the time of the transfusion
- 11. Hemoglobin measurement maximum 4 hours before the transfusion and at minimum 15 minutes before transfusion
- 12. Hemoglobin measurement 15 to 60 minutes after transfusion
- 13. Blood pressure every 15 minutes during the transfusion and until 15 minutes after the end of the transfusion
- 14. Heart rate every 15 minutes during the transfusion and until 15 minutes after the end of the transfusion
- 15. Body temperature every 15 minutes during the transfusion and until 15 minutes after the end of the transfusion
- 16. Respiratory rate every 15 minutes during the transfusion and until 15 minutes after the end of the transfusion
- 17. Oxygen saturation every 15 minutes and until 15 minutes after the end of the transfusion
- Patient diary for collection of concomittant medications and changes in health status from enrollment up to their following transfusion or 28 days (+/- 1 day) posttransfusion whichever comes first
- 19. Routine laboratory analyses, including blood gases when applicable.

11.1 Clinical investigation flow chart(s) / table of clinical investigation procedures and assessments

Investigation Periods	Screening & Enrollment Visit	Pre- Transfusi on	Transfusion	Post- Transfusion	Follow Up 1	Follow-up 2	Follow-up 3
Visit	1	2	2	2	3	4	5
Time (hour, day, week)	D0	D1	D1	D1	D2 (≤ 24h)	D7 (+/- 1 day)	Day of subsequent transfusion or D28, whichever comes 1 st
In- /Exclusion Criteria	x	x					
Patient Information							
Patient consent (ICF)	x						
Demographics	x						
Medical History	x						
Concomitant Medications	x	x	x	x	x	x	x
Physical Examination	x						x
Pregnancy Test	x						
Height	х						
Weight	x						
RBC Unit Weight		x					
Patient Hemoglobin		x		x			x
Blood Pressure	x	x	x	x			
Heart Rate	x	x	x	x			
Body Temperature	x	x	x	x			
Respiratory Rate	x	x	x	x			
Oxygen Saturation	x	x	x	x			
Transfusion			x				
Adverse Events, Adverse device effects	x	x	x	x	x	x	x
Review Device Integrity		x	x	x			
Patient Diary	x	x	x	x	X	x	

11.1.1 Hematogical Malignancies Group:

11.1.2 Burn patients Group:

Investigation Periods	Screening & Enrollment Visit	Pre- Transfus ion	Transfusion	Post- Transfusion	Follow Up 1	Follow-Up 2	Follow-Up 2
Visit	1	2	2	2	3	4	5
Time (hour, day, week)	Day 0	Day 1	Day 1	Day 1	Day 2 (≤ 24 h)	Day 7 (+/- 1 day)	Day of subsequent transfusion or D28, whichever comes 1 st
In- /Exclusion Criteria	x						
TBSA	x						
Patient Information							
Patient information and consent (ICF)	x						
Demographics	x						
Medical History	x						
Concomitant Medications	x	x	x	x	x		x
Physical Examination	x						x
Pregnancy Test	x						
Height	х						
Weight	x						
RBC Unit Weight		x					
Patient Hemoglobin		x		x			x
Blood Pressure	x	x	x	x			
Heart Rate	x	x	x	x			
Body Temperature	x	x	x	x			
Respiratory Rate	x	x	x	x			
Oxygen Saturation	x	x	x	x			
Transfusion			x				
Adverse Events, Adverse device effects	x	x	x	x	x		x
Review Device Integrity		x	x	x			

11.2 Assessments of outcomes

Patients will be monitored for adverse events throughout the entirety of their participation in the clinical investigation. Adverse events will be elicited from the patients, the medical record, and an adverse event diary, if applicable. Patients enrolled will undergo standard care for their disease/ illness as prescribed by the Investigators. All procedures will be performed in compliance with the site's established policies and work instructions. No additional assessments will be performed.

11.2.1 Assessment of primary outcome

Patients will be monitored for adverse events throughout the entirety of their participation in the clinical investigation. Investigators will monitor patients directly for adverse events during their transfusion visit. In addition, patients will be contacted by phone 24 hours and 7 days (+/- 1) after their transfusion visit to record any adverse events they have experienced since their transfusion visit. All adverse events will be recorded in the CRF and they will be assessed according to the instructions in section 12 of the CIP.

11.2.2 Assessment of secondary outcomes

For all secondary outcomes related to hemoglobin and vital sign measurements the sites will follow their standard practice.

For all secondary outcomes related to AE occurrence, investigators will monitor patients directly for adverse events during their transfusion visit and then patients will be contacted by phone 24 hours and 7 days (+/- 1) after their transfusion visit to record any adverse events they have experienced since their transfusion visit. The patient's chart will also be checked for any AE occurrence after their following transfusion visit or 28 days after their initial transfusion, whichever comes first. All adverse events will be recorded in the CRF and they will be assessed according to the instructions in section 12.

11.2.3 Assessment of other outcomes of interest

Not applicable.

11.2.4 Assessment of safety outcomes

See section 11.2.1 and 11.2.2 for information on assessment of safety outcomes.

11.2.4.1 Adverse events

See section 11.2.1 and 11.2.2 for information on assessment of adverse events.

11.2.4.2 Laboratory parameters

Local site staff will follow their standard procedures.

11.2.4.3 Vital signs

See section 11.2.2 for information on measurement of vital signs.

11.2.5 Assessments in subjects who prematurely stop the clinical investigation

All data from patients who withdraw/drop out of the study will be recorded up to and including their last visit before they withdraw their participation in the study.

11.2.6 Follow-up of the subjects after the regular termination of the clinical investigation All follow up of participants will be completed before the termination of the clinical investigation.

11.3 Procedures at each visit

11.3.1 Patient Information Contact

A Patient Information Sheet will be provided to prospective study participants by the PI or his designees. No information will be collected from prospective study participants during this contact.

11.3.2 Screening Visit

The following data will be collected during this visit:

- Inclusion/exclusion criteria
- Patient/legal representative informed consent
- Demographics
- Medical history
- Physical examination
- Pregnancy test
- Height
- Weight
- Blood pressure
- Heart rate
- Body temperature
- Respiratory rate
- Oxygen saturation
- Adverse event occurrence
- Concomitant medications
- Patient Diary

11.3.3 Transfusion Visit

The patients will receive a transfusion during this visit. The following data will be collected:

- RBC unit weight
- Patient hemoglobin pre- and post-transfusion
- Blood pressure during the transfusion and for 15 minutes post-transfusion
- Heart rate during the transfusion and for 15 minutes post-transfusion
- Body temperature during the transfusion and for 15 minutes post-transfusion
- Respiratory rate during the transfusion and for 15 minutes post-transfusion
- Oxygen saturation during the transfusion and for 15 minutes post-transfusion
- Infection occurrence
- Adverse event occurrence
- Concomitant medications
- Device deficiencies
- Patient Diary

11.3.4 First Follow-Up Visit

This visit will occur 24 hours post-transfusion and will be performed over the phone. The following data will be collected:

- Infection occurrence
- Adverse event occurrence
- Concomitant medications
- Device deficiencies
- Patient Diary

11.3.5 Second Follow-Up Visit

This visit will occur 7 days (+/- 1) post-transfusion and will be performed over the phone. The following data will be collected:

- Infection occurrence
- Adverse event occurrence
- Concomitant medications
- Device deficiencies
- Patient Diary

11.3.6 Final Follow-Up

This visit will occur at the patient's subsequent transfusion visit or 28 days (+/- 1 day) after their transfusion, whichever comes first. All data from this visit will be collected from the patient's chart. The following data will be collected:

- Adverse event occurrence
- Physical examination
- Concomitant medications
- Pre-transfusion hemoglobin (if applicable)

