6.3 Secondary Objectives

Secondary Objectives :

- A. For both patients groups
 - 1. Assessment of pre and post transfusion hemoglobin levels
 - 2. Assessment of hemoglobin level before the following transfusion, if applicable
 - 3. Assessment of AEs occurence:
 - i. Up to 7 days (+/- 1 day) post transfusion, in comparison with historical control (including but not limited to infection, deep vein thrombosis, acute respiratory distress syndrome, transfusion-related acute lung injury, transfusion associated circulatory overload, anaphylactic shock, acute haemolytic transfusion reaction).
 - ii. Up to the following tranfusion episode or up to 28 days (+/- 1 day) after the initial transfusion, whichever comes first.
 - From enrollment, up to their subsequent transfusion or 28 days (+/- 1 day) posttransfusion, whichever comes first, through the assessment of patient's diary
 - 4. Assessment of the vital signs during and up to 15 minutes after the transfusion
- B. For burn patients group only:
 - 1. Assessment of arterial blood gases:
 - i. pre-operative
 - ii. intra-operative
 - iii. post operative

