7.2 Secondary Outcomes

Secondary Outcomes : - for both patients groups

- 1. Evolution of the hemoglobin level before and after the transfusion.
- 2. Hemoglobin increment from transfusion corrected for patient blood volume and hemoglobin dose
- 3. Hemoglobin level before the following transfusion
- 4. Evaluate the frequency of all AEs, including transfusion related AEs up to 7 days (+/- 1) posttransfusion compared to historical data of patient registries (ex. The National Burn Registry)
- 5. Evaluate AEs up to 28 days after the initial transfusion, whichever comes first.
- 6. Evaluation the frequency of all AEs, from enrollment, up to 7 days (+/- 1 day) post transfusion, through the assessment of patient's diary, when applicable.
- 7. Evaluation of patient's vital signs over the course of the transfusion and up to 15 minutes posttransfusion

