3.3 Clinical investigation outcomes

3.3.1 **Primary outcome**

Number of participants who experienced an adverse event (all types/grades) from transfusion up to 24 hours and 7 days (+/- 1 day) post transfusion.

3.4 Secondary Outcomes:

1. Evaluation of blood pH, pO2, pCO2, HCO3 and base (excess) before, during and after the transfusion (Burn patients group only).

LINK Medical Study ID: HEM001

- 2. Hemoglobin level before the following transfusion
- 3. Frequency of all AEs, including transfusion related AEs up to 7 days (+/- 1) post-transfusion
- 4. AEs up to 28 days after the initial transfusion, or up to subsequent transfusion episode, whichever comes first.
- 5. Frequency of all AEs, from enrollment, up to 7 days (+/- 1 day) post transfusion, through the assessment patient's diary, when applicable.
- 6. Vital signs over the course of the transfusion and up to 15 minutes post-transfusion.

4 Study Design

This is a single center clinical trial of surgical bleeding in burn patients, and chronically transfused patients with haematologic malignancies. Patients are transfused with hypoxic red blood cells manufactured with Hemanext ONE system". The patient groups are burn patients and chronically transfused patients with haematologic malignancies. Patients need to be adults \geq 18. There will be no randomization of Patient s, no blinding, and no comparator.

A first cohort of 5 patients – solely from the hematological malignancies (chronically transfused) group - will be enrolled, transfused and followed-up until their subsequent transfusion or 28 days (+/- 1 day) post-transfusion, whichever comes first. All safety related data from this initial cohort of 5 patients will be reviewed and assessed by the clinical investigation Data Monitoring Committee (DMC). Upon favourable opinion from the clinical investigation DMC, the enrolment of the remaining patients (both groups) will resume until completion.

Each patient is expected to attend 5 visits:

- 1. Visit 1 (Screening): Determine eligibility and obtain baseline data, physical examination, and safety assessments.
- 2. Visit 2 (Transfusion Day):
 - a. Pre-Transfusion: eligibility, hemoglobin, and safety assessments
 - b. Transfusion: transfusion, safety assessments, and device integrity
 - c. Post-Transfusion: safety assessments, hemoglobin, and device integrity
- 3. Visit 3 Follow-Up (24 hours post-transfusion): safety assessments and device integrity

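### The documents disagree on whether the diary runs to Day 7 or to the next transfusion or Day 28, and the detailed procedures leave adverse events after Day 7 to the chart

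*Protocol*

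**What the plan says.** **Passages that run the diary to the next transfusion or Day 28**
- Protocol 6.3, A.3.iii, on diary-assessed AEs: "From enrollment, up to their subsequent transfusion or 28 days (+/- 1 day". The synopsis objective and SAP 3.2 (B.3.iii) have the same window.
- Protocol synopsis, secondary outcome 6: same window.
- Protocol 11, list of information collected: "Patient diary for collection of concomittant medications and changes in health status from enrollment up to their following transfusion or 28 days".
- Protocol synopsis, haematology schedule: the diary is ticked in every column, including Visit 5.

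**Passages that stop it at Day 7 or Visit 4**
- Protocol 7.2 item 6: "Evaluation the frequency of all AEs, from enrollment, up to 7 days (+/- 1 day) post transfusion".
- SAP 3.4 item 5: "Frequency of all AEs, from enrollment, up to 7 days (+/- 1 day) post transfusion".
- Protocol 11.1.1 and SAP Appendix A: the diary row is ticked for Visits 1 to 4 and blank at Visit 5.
- Protocol 11.3.6: the diary is not among the items collected at the final follow-up.

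**How AEs after Day 7 are found**
- Protocol 11.2.2 gives phone contacts at 24 hours and Day 7, and then: "The patient's chart will also be checked for any AE occurrence after their following transfusion visit or 28 days after their initial transfusion".
- Protocol 11.3.6, on Visit 5: "All data from this visit will be collected from the patient's chart".
- Protocol 11.2, in contrast, names the patients, the medical record and (where applicable) a diary as AE sources over the whole of participation.

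**The concern.** A stated secondary objective, diary AEs to the next transfusion or Day 28, has no matching outcome in Protocol 7.2 or SAP 3.4, and no matching collection step in the detailed visit procedures. A site works from the visit instructions and an analyst from the SAP. Both would then leave an already issued diary unused after about Day 7.

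This matters because the study exists to collect preliminary safety data. Section 8.1 calls it the first use of hypoxic blood made with this device. Section 12.3 lists delayed reactions among the expected events. The sample size is justified in 13.2 and SAP 5.1 on the ground that unexpected AEs will be identified, which depends on how AEs are looked for. The DMC decides whether to open the rest of enrolment, including the burn group, from five haematology patients followed to the next transfusion or Day 28. A low late AE count in those five could mean few events, or it could mean that nobody had read the diary.

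**Working it through.** The plan gives no figure to reproduce here. The check is a comparison of passages, followed by the length of the exposed period.

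**1. The two versions side by side**

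| Item | Next transfusion or Day 28 | Day 7, or not at Visit 5 |
|---|---|---|
| Diary objective | Synopsis; Protocol 6.3; SAP 3.2 | none |
| Diary outcome | Synopsis outcome 6 | Protocol 7.2 item 6; SAP 3.4 item 5 |
| Diary keeping | Synopsis list; Protocol 11 list | none |
| Diary at Visit 5 (haematology) | Synopsis schedule | Protocol 11.1.1; SAP Appendix A; Protocol 11.3.6 |
| AE source after Day 7 | Protocol 11.2: patient, record, diary | Protocol 11.2.2 and 11.3.6: chart |

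**2. Is the omission in 11.3.6 just shorthand?** Probably not. The lists for the two phone visits, 11.3.4 and 11.3.5, both name the diary; the list in 11.3.6 does not. SAP section 4 gives safety assessments for Visits 1 to 4, but only haemoglobin and physical examination for Visit 5. SAP 6.1.1 names phone contact at Visits 3 and 4 only.

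**3. Is the shorter window a recorded change?** No. SAP 8.1 lists two modified or excluded secondary objectives, and the diary window is not one of them.

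**4. Completers and drop-outs.** Protocol 13.5 has investigators try to contact transfused patients who drop out about AEs to the next transfusion or Day 28. No equivalent contact after Day 7 is stated for patients who stay in.

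**5. Burn group.** The synopsis intervention lists the diary for both populations. Neither burn schedule in the Protocol, nor SAP Appendix B, has a diary row.

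**6. Length of the exposed period.** Day 8 to Day 28 is 28 − 8 + 1 = 21 days, and 21/28 = 75%. This is a maximum. It shrinks when the next transfusion comes sooner: 5.1.5 describes roughly weekly transfusion in intensive treatment, so some haematology patients may have almost no time after Day 7. Section 5.5 ends AE collection for burn patients at discharge if that is earlier.

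**7. Illustration only.** Let p be the true chance that a patient has a late AE and c the share that the chart captures. The documents give neither; both are assumptions. The chance that at least one late AE is recorded among n patients is 1 − (1 − p·c)^n:

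| n | p | c = 1.0 | c = 0.75 | c = 0.5 |
|---|---|---|---|---|
| 10 | 5% | 40% | 32% | 22% |
| 10 | 10% | 65% | 54% | 40% |
| 10 | 20% | 89% | 80% | 65% |
| 20 | 5% | 64% | 53% | 40% |
| 20 | 10% | 88% | 79% | 64% |
| 20 | 20% | 99% | 96% | 88% |

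For example, with n = 20, p = 10% and c = 0.5: 1 − 0.95^20 = 64%, against 1 − 0.90^20 = 88% with full capture. The table shows only that incomplete capture could matter at this sample size. It does not estimate the loss.

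**The case against.** A reader might infer that nobody asks the patient after Day 7. The documents do not support that as a fact. Section 11.2 names patients and diary as sources, SAP 6.1.1 runs AE monitoring to Visit 5, and the synopsis schedule collects the diary there. A physical examination and a haemoglobin value are also scheduled at Visit 5, and the synopsis visit diagram appears to label the last visit as on site. If those take place, the patient is seen, and the chart may simply be the source document of a real visit. This stands: chart-only collection is one of two conflicting versions. But none of these passages tells the site to review the diary or ask about AEs at Visit 5, and 11.2.2 and 11.3.6 tell it where to look instead.

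A reader might also infer that the diary outcome was deliberately shortened. Nothing shows this: synopsis outcome 6 and every diary objective keep the longer window, and SAP 8.1 records no change. It is an unreconciled contradiction.

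Three further points stand. A delayed serologic reaction is a laboratory finding that a diary or phone call would not reveal, so the case rests on symptomatic events. SAP 7.8.1 already has an overall AE row, which covers AEs from all sources to the end of follow-up. And this is a descriptive pilot without a hypothesis, whose primary outcome closes at Day 7.

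**Conclusion.** The contradiction is real and should be corrected before the plan is used. If the detailed procedures are followed, diary entries after Day 7 are not collected, the diary objective in Protocol 6.3 and SAP 3.2 cannot be answered, and AEs between Day 8 and the next transfusion or Day 28 may be under-recorded. The exposed span is at most 21 of 28 days.

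A reader might want a percentage for the under-count. None can be derived: any such figure only restates an assumed capture rate for the chart. That under-recording will occur is plausible but not shown.

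The items affected are the secondary 28-day AE outcome, the diary-based AE summary and the DMC review of the first five patients. The primary outcome is not affected. For burn patients the conclusion about the diary is conditional, because the documents do not settle whether they keep one.

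**What to change.** - **Protocol 11.3.6, 11.2.2 and 11.1.1, and SAP Appendix A:** add diary return and review, and AE questioning of the patient, at Visit 5. Do this in person at the next transfusion or the Visit 5 examination, otherwise by phone. Section 11.2.2 must be changed with the rest, or its chart check after Day 7 will contradict the new text.
- **Protocol 11.3.6:** replace the sentence that takes all Visit 5 data from the chart with one naming patient, diary and chart as sources, in line with 11.2.
- **Protocol 7.2 item 6 and SAP 3.4 item 5:** set the window to the next transfusion or Day 28, whichever is first, to match the objective.
- **SAP 7.8.1:** give the diary-based AE summary that same window. No new row for all-source AEs is needed.
- **Burn group:** reconcile the synopsis intervention with the burn schedules and state whether these patients keep a diary.

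The cost is wording, plus at most one phone call for each patient not seen at Visit 5. The diary is already planned for the longer period.
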